6.11 Primary Endpoints

Peak FEV₁ (measured in first 4 hours after dosing) and AUC_{0-12h} FEV₁. These will be measured after dosing on Day 3

The peak effect on FEV_1 during these time intervals will be computed as the maximum value within the 4 hours after dosing minus the pre-dose Day 1 baseline value.

The average effect will be calculated as the AUC divided by the length of the time interval of interest. The AUC parameters will be calculated using the linear trapezoidal rule.

Pre-dose treatment day 1 value for each treatment period will be used as the baseline value.

Changes from baseline in AUC average effect parameters will be derived by deducting the pre-dose treatment day 1 value from the average effect.

Peak effect and average effect will be log_e transformed in order to perform a multiplicative (Analysis of Covariance) ANCOVA as follows:

Log_e (Max FEV₁)

 Log_e (AUC_{0-12h} FEV₁ /12)

Spirometry performed within 8 hours after the use of a rescue bronchodilator (salbutamol) will not be utilized in calculations of peak or AUC FEV_1 .

Observed FEV_1 data will be summarised as actual and change from baseline using descriptive statistics over time.

Hypothesis to be tested:

 H_0 = tiotropium + RPL554 in patients with COPD has the same effect on FEV₁(first 4 hours)/ AUC_{0-12h} FEV₁ as tiotropium + Placebo

The primary comparisons are tiotropium + RPL554 6mg vs tiotropium + RPL554 placebo, followed by tiotropium + RPL554 1.5mg vs tiotropium + RPL554 placebo.

All hypothesis testing will be done using two-sided alternative hypotheses. P-values less than 5% will be considered statistically significant.

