	Male and female patients with moderate to severe COPD, with a post-bronchodilator FEV_1 of 40 to 80% of predicted. They must have a baseline increase in FEV_1 of ≥ 150 mL after use of four puffs of salbutamol. They must have at least a 10 pack-year smoking history, and may be an ex-smoker or current smoker.
	Exclusion Criteria
	Patients must be clinically stable without recent COPD exacerbations or hospitalisations. They must not have uncontrolled disease or chronic heart failure.
Study Treatments:	All study treatments will be administered using the inhaled route.
	Patients will receive the following three dose treatment combinations (DPI treatment plus nebulised treatment) in a randomised sequence during Treatment Periods 1 to 3:
	Tiotropium 18 μg once daily + RPL554 6 mg twice daily Tiotropium 18 μg once daily + Placebo twice daily Tiotropium 18 μg once daily + RPL554 1.5 mg twice daily
	Each morning during each 3 day period, the DPI treatment (tiotropium; Spiriva [®] HandiHaler [®]) will be administered first followed immediately (starting within 2 minutes) by the nebulised treatment (RPL554 or placebo). The nebulised treatment (RPL554 or placebo) only will be repeated in the evening on Day 1 and Day 2, 12 hours after the morning dose; there is no evening dose of study treatment on Day 3 of each treatment period.
	The DPI treatment will be administered open label and the nebulised treatment will be administered double blind.
	The nebulised treatment (RPL554 or placebo) will be administered using a standard Jet nebuliser (PARI LC SPRINT [®] plus a PARI TurboBOY [®] SX compressor unit).
	The RPL554 formulation is a sterile suspension supplied as sterile stock suspensions of micronised RPL554 in pH 7 phosphate buffered saline, containing surfactants to aid suspension. The placebo is the same as the RPL554 suspension except that the active RPL554 ingredient is omitted, i.e. it consists of pH 7 phosphate buffered saline and surfactants only. It is thus a clear solution rather than a pale yellow suspension; there is no known inert yellow solid that would be acceptable for inhalation, and therefore a visually matching placebo could not be developed.

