5.9.1 Prior and Concomitant Therapies

All prior therapies for COPD taken in the 3 months prior the first study treatment administration and all concomitant COPD therapies for will be recorded in the eCRF, with the medication, dose, route and start and stop date(s) and time(s) clearly recorded to document all required washout periods and compliance with the inclusion and exclusion criteria.

Oral therapies for COPD (e.g. oral steroids, theophylline, and roflumilast) are not allowed in the 3 months prior to screening and throughout the study. Inhaled steroids may continue during the study at a maintenance dose.

All long acting (once or twice daily) bronchodilators will be stopped at the screening visit and are not allowed during the study. Patients should not use a long acting bronchodilator (long acting muscarinic antagonists [LAMA], long acting beta2-agonists [LABA], or combination LABA/inhaled steroid) on the day of screening.

Patients taking LAMAs and LABAs should be placed on short acting bronchodilators (e.g. salbutamol, ipratropium or Combivent[®]) as per the discretion of the Investigator. These can be dosed on a regular scheduled basis and/or as needed use. Patients taking LABA/inhaled steroid combination products should be prescribed the inhaled steroid at the same or equivalent dose contained in the combination product to allow continuation of steroid use regularly throughout the study whilst stopping the LABA component. Patients currently taking terbutaline will be switched to other short acting bronchodilators (e.g. salbutamol).

If this is inadequate to control their symptoms, they should contact the Investigator. No scheduled use of salbutamol or ipratropium is allowed during the 3-day treatment periods; but may be used as a rescue medication (see Section 5.10). Salbutamol and ipratropium (or Combivent[®]) must be withheld for at least 8 hours prior to spirometry and this confirmed in the eCRF at the start of each treatment period. If this withhold is not met, the patient should be rescheduled for a repeat visit within permitted windows. Short acting bronchodilators

should be withheld during each treatment period for the time periods stated below unless absolutely necessary:

- 8 hours prior to pre-dose spirometry for Day 1, Day 2 and Day 3.
- Post-dose:
 - Day 1 until after +12 hours spirometry
 - Day 2 until after + 4 hours spirometry
 - Day 3 until after + 24 hours spirometry

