5.10 Rescue Medications

Standard procedures for emergency care should be followed for any individual adverse event, whenever clinically needed (decision to be taken by the Investigator). Short acting bronchodilators (e.g. salbutamol, ipratropium or Combivent) may be used as rescue medication. Rescue medication (salbutamol and ipratropium) will be sourced by the study centre and both will be dispensed at the screening visit. Salbutamol should be considered the primary rescue medication and ipratropium secondary.

Rescue medication use during each treatment period must be separately documented on the eCRF (medication, dose, route, date and time of each administration). Protocol procedures must still continue even if rescue medication has been taken. Salbutamol is to be used for primary rescue use.

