6.12 Secondary Endpoints

The following endpoints will be analysed based on the FAS:

AUC_{0-4h} FEV₁ after morning dosing on Day 1, Day 2 and Day 3

Log_e (AUC_{0-4h} FEV₁/4)

Peak FEV₁ (measured in first 4 hours after dosing) and AUC_{0-12h} FEV₁ Day 1

Peak effect and average effect will be \log_e transformed in order to perform a multiplicative ANCOVA as follows:

Log_e (Max FEV₁)

Log_e (AUC_{0-12h} FEV₁/12)

Onset of action

Time to onset of action will be determined for each patient on Day 1 of each treatment period. The scheduled timepoint at which $\geq 10\%$ increase from baseline was achieved and the scheduled timepoint before that will be interpolated to determine the time relative to dosing at which 10% increase occurred for that patient on that treatment day. Subjects who do not achieve a 10% increase from baseline by 120 minutes (2 hours postdose) on Day 1 will be censored.

The following formulae will be used to derive the time to onset:

Time to Onset = Time A + (FEV₁ target - FEV₁ A)/ (FEV₁ B - FEV₁ A) * (Time B - Time A)

Where:

- Time A is the scheduled timepoint before 10% increase is met
- Time B is the scheduled timepoint at which 10% increase is met
- FEV₁ target is the FEV₁ value corresponding to a 10% increase or, if FEV₁ is expressed as percentage increases from baseline, it is the value 10 itself
- FEV_1 A is the maximum FEV_1 measurement at the timepoint before 10% increase is met
- FEV₁ B is the maximum FEV₁ measurement at the timepoint at which 10% increase is met

RV, FRC, sG_{aw} and R_{aw} at 1.25 hours after dosing on Day 2

Ability to adequately perform whole body plethysmography will be conducted at screening. Whole body plethysmography assessments will be conducted at pre-dose Day 1, pre-dose and 1.25 hours post-dose on Day 2 of each treatment period. Patients will be placed on a body box for plethysmographic determination of lung volumes, to include RV, FRC and total lung capacity (TLC). Additionally,

measurements will be made of airway conductance (sG_{aw}) and airway resistance (R_{aw}).

Plethysmographic endpoints will be calculated on Day 2, at both pre-dose and 1.25 hours post dose of each treatment period. The change from pre-dose Day 1 will be calculated for RV, FRC, sG_{aw} and R_{aw} at 1.25 hours post-dose on Day 2 of each treatment period.

AUC, C_{max}, t_{max} and half-life

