6.13.1 Exploratory Analysis

Log_e (pre-dose FEV₁) on Day 3 will be compared between the three study treatments using analysis of covariance (ANCOVA) models with fixed factors for treatment, period and patient, and using the baseline measurement of the treatment day (pre-first dose in a treatment period) as a covariate. The analysis uses multiplicative models and the result will be transformed back to the linear scale giving treatment differences as ratios of geometric means.

The combination of tiotropium + RPL554 will be compared to Placebo tiotropium + RPL554 for each of the two doses of RPL554. Results of the comparisons will be expressed as the mean geometric ratio with 95% confidence intervals and associated, 2-sided, p-value.

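### The SAP drops post-rescue readings from peak and AUC FEV1 only, so by default they still count in Day 1 onset, Day 2 plethysmography and Day 3 pre-dose FEV1

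*SAP*

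**What the plan says.** The only rescue rule for analysis is in SAP 6.11: "Spirometry performed within 8 hours after the use of a rescue bronchodilator (salbutamol) will not be utilized in calculations of peak or AUC" FEV1. Its wording also reaches the secondary peak and AUC endpoints of SAP 6.12 (Day 1 peak and AUC0-12h; AUC0-4h on Days 1 to 3).

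Three other lung-function derivations carry no rescue condition:

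- Onset on Day 1 (SAP 6.12) is censored for one reason only: "Subjects who do not achieve a 10% increase from baseline by 120 minutes (2 hours postdose) on Day 1 will be censored".
- Plethysmography (SAP 6.12): "Plethysmographic endpoints will be calculated on Day 2, at both pre-dose and 1.25 hours post dose of each treatment period".
- Trough (SAP 6.13.1): log pre-dose FEV1 "on Day 3 will be compared between the three study treatments using analysis of covariance (ANCOVA) models".

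Neither SAP 6.2 nor SAP 6.19 extends the rule, and SAP 6.2 has all available data summarised.

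On conduct, Protocol 5.10 says "Short acting bronchodilators (e.g. salbutamol, ipratropium or Combivent) may be used as rescue medication" and "Protocol procedures must still continue even if rescue medication has been taken". Protocol 5.9.1 limits use: short-acting bronchodilators "should be withheld during each treatment period for the time periods stated below unless absolutely necessary". The listed periods are the 8 hours before pre-dose spirometry on Days 1, 2 and 3, and after dosing up to the 12-hour (Day 1), 4-hour (Day 2) and 24-hour (Day 3) spirometry. Rescheduling for a missed withhold is tied to the check at the start of each treatment period. Protocol 5.9.2 and 10.2 let the pre-lock review exclude patients or particular data.

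**The concern.** The SAP has already decided that a reading within 8 hours after rescue salbutamol does not measure the randomised treatment. It applies that decision to peak and AUC but not to onset, trough or plethysmography, so the same data can be rejected for one endpoint and used for another.

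The population makes this matter. Of eligible patients, the Protocol synopsis says: "They must have a baseline increase in FEV_1 of ≥ 150 mL after use of four puffs of salbutamol". If rescue use differs between treatments, part of a between-treatment difference in these endpoints would be a salbutamol effect. Trough and plethysmography rest on single assessments, so one affected value is the whole outcome for that patient and period. Onset, lung volumes and the Day 3 trough dose response are all named secondary objectives, and p-values are planned.

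**Working it through.** **1. Coverage, endpoint by endpoint**

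| Endpoint | Rescue condition in SAP | Withholding in Protocol 5.9.1 |
|---|---|---|
| Peak and AUC FEV1 | Yes, 8 h after salbutamol | Yes |
| Onset, 0 to 120 min, Day 1 | None | Yes, to +12 h |
| Plethysmography, 1.25 h, Day 2 | None | Yes, to +4 h |
| Pre-dose FEV1, Day 3 | None | Yes, 8 h before |

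The withholding allows exceptions in all these rows. The start-of-period check protects the Day 1 baseline, not Day 2 or Day 3 values. Rescue is dispensed at screening, and patients may go home on the nights after Days 1 and 2.

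**2. One reading, two treatments**

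Take a baseline of 1.3 L, so the onset target is 1.1 × 1.3 = 1.43 L. Suppose FEV1 at 1 h is up 5% (1.365 L), salbutamol is taken at 65 minutes, and the 1.5 h reading is 150 mL higher (1.515 L). SAP 6.11 drops the 1.5 h reading from Day 1 peak and AUC. The SAP 6.12 formula uses it:

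onset = 60 + (1.43 − 1.365)/(1.515 − 1.365) × 30 = 73 minutes.

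Had the salbutamol been taken at 75 minutes, the interpolated onset would come before the rescue. A remedy must therefore act on readings, not on the computed time.

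On Day 2, after rescue at 30 minutes, spirometry at 1 h and 2 h is dropped from AUC0-4h, while plethysmography at 1.25 h is kept.

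**3. The plan's own design figure**

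Inputs (Protocol 10.5, SAP 3): residual CV 6%, 24 patients, 80% power, baseline 1.3 L; two-sided 5% level.

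- Log-scale SD = √ln(1 + 0.06²) = 0.0599; SE of a pairwise contrast = 0.0599 × √(2/24) = 0.0173.
- Residual df = 72 − 1 − 23 − 2 − 2 − 1 = 43. Noncentral t gives a detectable log difference of 0.0496, a ratio of 1.051.
- Power at 5.1% is 80.2%; 0.051 × 1.3 L = 66 mL.

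The stated 5.1% and 66 mL are reproduced. They serve only as a yardstick.

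**4. Scale for onset**

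150/1300 = 11.5%, against a threshold of 10%. A 150 mL rise reaches 10% at any baseline up to 150/0.10 = 1500 mL.

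**5. Scale for trough (illustrative)**

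Assume a net excess of a fraction q of placebo periods with rescue in the 8 hours before the Day 3 trough, and a remaining gain of g mL. Neither is in the documents. With b = q × ln(1 + g/1300), the placebo mean shifts by exp(b) − 1, and a true 5.1% effect is estimated as 1.051/exp(b) − 1. Power uses noncentrality (ln 1.051 − b)/0.0173, borrowing the peak CV.

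| q | g = 75: shift; estimate; power | g = 150: shift; estimate; power |
|---|---|---|
| 1/24 | 0.2% (3 mL); 4.9%; 76% | 0.5% (6 mL); 4.6%; 72% |
| 3/24 | 0.7% (9 mL); 4.4%; 68% | 1.4% (18 mL); 3.7%; 53% |
| 6/24 | 1.4% (18 mL); 3.6%; 52% | 2.8% (36 mL); 2.3%; 24% |

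If the excess falls on RPL554 instead, the estimate rises: for q = 3/24 and g = 150, 1.051 × 1.0137 − 1 = 6.5%.

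**The case against.** The case for leaving the SAP alone has several parts.

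- **Exposure is limited.** The withholding covers all three windows, so the problem needs an exception at a particular moment. This stands: affected values should be few.
- **Review before lock.** The pre-lock review, held under blind, can remove data, and rescue use is summarised by treatment, so an imbalance would be seen. This stands in part: the review has no stated criterion for rescue, so handling would be decided case by case.
- **Tiotropium may already produce onset.** The label in Protocol 15.1 reports a mean FEV1 rise of 0.13 L (13%) at 30 minutes after the first dose, in a different population. Many patients in every arm may pass 10% before any rescue. This stands, and weakens the onset example.
- **The 150 mL is generous.** It was measured 20 to 30 minutes after 400 mcg at screening, not on top of tiotropium, and must wane over 8 hours. This stands: gains below 75 mL are possible.
- **Exclusion is not neutral.** The values lost may come from poorer responders, so using all data is also defensible. This stands, and is why both analyses should be reported.

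A reader might infer that the gap favours placebo and hides a real RPL554 effect. The documents do not support that: they give no rescue frequency by treatment, and an excess on RPL554 would inflate the effect. Nor does the gap touch the primary endpoints, which the rule covers for salbutamol.

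**Conclusion.** The gap is real and follows from the text alone: post-rescue readings are excluded from peak and AUC FEV1 and, by default, kept for onset, plethysmography and Day 3 pre-dose FEV1. This is an inconsistency in the SAP's own rule rather than merely a missing detail.

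Its likely effect is small. The endpoints are secondary and treated as descriptive (SAP 6.15) or exploratory. The direction of bias is unknown. The 11.5% against 10% comparison shows that one response to rescue could by itself count as onset in a typical patient, provided the screening response carries over to a patient already on tiotropium. The trough table shows sensitivity to assumed inputs; it is not an estimate of what will happen. The point concerns which endpoints the rule covers, not which rescue drugs it names.

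**What to change.** In the SAP, before unblinding, apply the 6.11 exclusion to all lung-function endpoints:

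- **Onset.** Do not use post-rescue readings to define onset. A patient whose readings before rescue show no 10% rise counts as not achieving onset by 120 minutes: censored at 120 minutes in the Kaplan-Meier analysis, and ranked with the non-achievers in the Wilcoxon signed rank test. Censoring at the rescue time should be avoided: entered in that test at 45 minutes, such a patient could rank as faster than one censored at 120 minutes.
- **Day 3 pre-dose FEV1.** Set to missing if rescue was used in the preceding 8 hours.
- **Day 2 plethysmography.** Do the same.
- **Sensitivity.** Report the all-data analysis of each endpoint alongside.

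The cost is a paragraph of SAP text. Rescue dates and times are already recorded in the eCRF (Protocol 5.10), and no rule on rescue use changes. A few values are lost, possibly from poorer responders; the sensitivity analysis would show whether that matters.

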10.2 Populations to be Analysed

Allocation of patients to the analysis populations (and whether any patients or specific data from a patient will be excluded) will be determined at the pre-database lock meeting.

The full analysis set will consist of all randomised patients with sufficient data collected after intake of study treatment to compute the pharmacodynamic parameters on at least two treatment periods. A completer analysis set will consist of all randomised patients that complete all visits.

The safety set will consist of all randomised patients who took at least one dose of study treatment during at least one visit.

The pharmacokinetic data set will consist of all randomised patients with blood sampling performed after at least one dose of RPL544 and with data sufficient to calculate pharmacokinetic parameters.

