6.2 Derived data

• Definition of baseline

Baseline is defined as the last non-missing value (including scheduled and unscheduled assessments) prior to the patient receiving study treatment for each of the respective study treatments.

For ECG and vital signs, time-matched baselines from Day 1 of each Treatment Period will be used for the analysis of data.

Incomplete dates

For calculation purposes, incomplete dates will be completed using worst case. Further details are detailed in the relevant sections as required.

• Non-numeric values for numeric variables

In the case where the result of a variable is recorded as ">x", " \ge x", "<x" or " \le x", then for analysis purposes a value of x will be taken. Where a range of values is quoted the midpoint of the range will be taken.

• Methods for handling withdrawals and missing data

Patients withdrawn after only one treatment period will not be included in the efficacy analyses. If a patient has baseline data missing for a parameter, within a treatment period, data for that patient and parameter will not be derived or analysed for that treatment period.

No imputation of missing data will be performed.

All available data from all dosed patients who have received study treatment will be listed and summarised. Any unscheduled or unplanned readings will be presented within the patient listings, but only the scheduled readings will be used in any summaries. If a treatment day is rescheduled due to variability in FEV_1 or other reason, the rescheduled treatment day will be listed and summarised as the valid treatment day.

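### The 8-hour post-rescue exclusion in SAP 6.11 names only salbutamol; read literally, FEV1 readings after permitted ipratropium rescue stay in peak and AUC

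*SAP*

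**What the plan says.** The exclusion rule is in SAP 6.11: "Spirometry performed within 8 hours after the use of a rescue bronchodilator (salbutamol) will not be utilized in calculations of peak or AUC" FEV1. Only one drug is named.

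The permitted rescue list is wider. Protocol 5.10 states "Short acting bronchodilators (e.g. salbutamol, ipratropium or Combivent) may be used as rescue medication", and SAP 6.12 repeats this. Both set an order of use: "Salbutamol should be considered the primary rescue medication and ipratropium secondary". Protocol 5.10 has both drugs dispensed at screening.

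Protocol 5.9.1 treats the drugs alike before spirometry: "Salbutamol and ipratropium (or Combivent[®]) must be withheld for at least 8 hours prior to spirometry". Within the treatment periods, short acting bronchodilators "should be withheld during each treatment period for the time periods stated below unless absolutely necessary"; on Day 3 this runs to the 24-hour reading. If rescue is nevertheless taken, "Protocol procedures must still continue even if rescue medication has been taken".

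Neither document has a separate rule for readings after ipratropium, and SAP 6.19 (changes from the protocol) does not mention the exclusion. SAP 6.2 adds: "No imputation of missing data will be performed".

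**The concern.** The 8-hour withhold in Protocol 5.9.1 implies that salbutamol, ipratropium and Combivent can each disturb FEV1 for that long. The SAP's exclusion after rescue should then cover the same drugs. As worded, it supports two derivations of Day 3 peak and AUC0-12h FEV1 from the same data: one drops readings after any rescue bronchodilator, the other only after salbutamol. It also leaves open whether Combivent counts as salbutamol, since the documents do not give its composition.

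What is at stake is dilution. A placebo period that keeps readings raised by ipratropium raises the placebo mean and shrinks the estimated RPL554 effect on both primary endpoints. That follows only if such use is commoner on placebo, which the documents neither state nor rule out.

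**Working it through.** **Yardstick.** SAP section 3 gives a residual CV of 6%, 24 patients, 80% power and a detectable difference of 5.1%, about 66 mL at a baseline of 1.3 L. Check: SE of a pairwise log difference = 0.06 × √(2/24) = 0.0173. A noncentral t calculation with 44 df, two-sided 5%, gives a detectable ratio of 1.0509, that is 5.1%; 0.051 × 1.3 L = 66 mL. The plan's figure reproduces and is not in question.

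**Trapezoid weights.** Day 3 readings up to 12 h are pre-dose, 5, 15 and 30 min, and 1, 1.5, 2, 4, 6, 8 and 12 h (Protocol 7.2.1). I take the Day 3 pre-dose reading as time 0. Each interior reading has a weight of half the gap between its neighbours:

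- pre-dose: (5/60)/2 = 0.04 h
- 4 h: (6 − 2)/2 = 2 h
- 6 h: (8 − 4)/2 = 2 h
- 8 h: (12 − 6)/2 = 3 h
- 12 h: (12 − 8)/2 = 2 h

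**Assumption.** The gain from ipratropium on top of tiotropium is not in the documents. I take 0 to 100 mL, constant for 8 hours, and show the ceiling. All lower limits are 0.

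**Ipratropium with no earlier post-dose salbutamol.**

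- Just after the 2 h reading: the 4, 6 and 8 h readings are affected, weight (2 + 2 + 3)/12 = 7/12.
- Just after dosing: 5 min to 8 h are affected, weight (12 − 0.04 − 2)/12 = 0.83.
- Peak: if an affected reading within 4 h is the maximum, the peak can rise by the full 100 mL.

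**Ipratropium after post-dose salbutamol (the protocol's order).** Salbutamol at any time before 4 h already removes every later reading up to and including 8 h, so peak cannot be affected. Only the 12 h reading can escape, and only if salbutamol is taken before 4 h and ipratropium after 4 h. Its weight is 2/12 on the planned grid. If the trapezoid bridges the dropped readings, the weight is 5/12 (from 2 h to 12 h) to 6/12 (from pre-dose to 12 h).

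**Size at the 100 mL ceiling.** Per-period shift = weight × 100 mL. Shift in the placebo mean for one period of 24 = that ÷ 24.

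| Case | Per period (mL) | Placebo mean (mL) | Share of 66 mL |
|---|---|---|---|
| AUC average, just after 2 h | 58.3 | 2.4 | 3.7% |
| AUC average, just after dosing | 83.0 | 3.5 | 5.2% |
| Peak | 100 | 4.2 | 6.3% |
| AUC average, after salbutamol, planned grid | 16.7 | 0.7 | 1.1% |
| AUC average, after salbutamol, bridged | 41.7 to 50.0 | 1.7 to 2.1 | 2.6% to 3.2% |

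These are arithmetic means in mL; the model works with log FEV1, so they show scale only. The bias in the treatment contrast grows with the excess of affected placebo periods over affected RPL554 periods, a count the documents do not give.

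**Opportunity for use.** The Protocol 5.9.1 withhold covers 12 + 8 + 4 + 8 + 24 = 56 of the 72 hours of a period (Day 1 to 12 h; 8 h before Day 2; Day 2 to 4 h; 8 h before Day 3; Day 3 to 24 h). The whole Day 3 window lies inside it, so use there should be uncommon.

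**The case against.** The strongest reply is that the operative words in SAP 6.11 are the general ones, a rescue bronchodilator. SAP 6.12 describes rescue as including ipratropium and Combivent, so the parenthesis most naturally names the first-line drug. That is plausible, and nothing shows that the sponsor chose to keep readings after ipratropium. But SAP 6.12 marks its list as examples and SAP 6.11 does not, so the literal reading stays open.

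Second, the matter can be settled before lock. Protocol 10.2 says that "whether any patients or specific data from a patient will be excluded) will be determined at the pre-database lock meeting", and Protocol 5.8 keeps the blind until then. This makes a treatment-driven choice unlikely. It is still case-by-case discretion and not a stated derivation rule.

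Third, the effect is small and conditional. That stands. In the protocol's order of use peak is untouched, and the affected share of the AUC is limited to the 12 h reading.

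A reader might also infer from the tiotropium label in Protocol Appendix 15.1 (label 7.2) that ipratropium should be barred as rescue. The label text concerns anticholinergic adverse effects, not FEV1 derivation, and keeping ipratropium as second-line rescue is an explicit clinical choice. It is not part of this point.

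**Conclusion.** The mismatch is real and minor. Taken literally, SAP 6.11 keeps any post-ipratropium readings in peak and AUC FEV1. With no ipratropium use the effect is zero. At the assumed 100 mL ceiling, one affected placebo period in 24 moves the placebo mean 12-hour average by up to about 2.4 to 3.5 mL and the placebo mean peak by up to about 4.2 mL, against 66 mL. Peak is affected only when ipratropium is taken without earlier post-dose salbutamol.

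A reader might infer that the primary result is biased, or could be a false positive. The documents do not support either. They give no rescue rates by treatment, and the mechanism favours RPL554 only if ipratropium is used more often on RPL554 than on placebo. Nor do they settle that the rule reaches the secondary endpoints. The sentence stands under the primary endpoints; its wording is general, but SAP 6.12 does not repeat it for Day 1 peak and AUC0-12h or for AUC0-4h.

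**What to change.** In SAP 6.11, delete the parenthesis naming salbutamol, or replace the phrase with any short acting rescue bronchodilator, giving salbutamol, ipratropium and Combivent as examples. Keep the list open, because the rescue lists in Protocol 5.10 and SAP 6.12 are themselves only examples; a closed list would leave the same kind of gap. Add that the rule applies to all peak and AUC FEV1 endpoints, primary and secondary.

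The cost is a few words. No new data are needed, because Protocol 5.10 already requires the drug, dose, route, date and time of each rescue use. The drawback is that a few more readings are dropped without imputation. Ipratropium just after 2 h would leave no reading between 2 h and 12 h, and use after 4 h would remove the 12 h reading that closes the AUC. Both already happen after salbutamol, so the change extends an accepted cost to the other rescue drugs.
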